HCV viral load (patients with prior history of HCV only)	x	Every 4 th cycle, (ie, C4D1, C8D1, C12D1, C16D1, C20D1, C24D1, C28D1, C32D1, C36D1)	-	-	Patients who completed treatment for HCV at least 6 months prior to screening and have no detectable circulating HCV during screening, may participate in the study. Such patients will be required to undergo assessment for HCV reactivation as shown and will be withdrawn from the study if they test positive at any time during the study.
HBV serology	x	-	-	-	All patients will be tested for HBsAg, antibody to antiHBs, and antibody to antiHBc assessments performed locally prior to the first dose.
HBV-DNA testing	x	Q12W during treatment	x	Q12W for up to 6 months after the last dose of study treatment	Only required for patients (in all treatment arms) with serologic evidence of prior HBV infection (ie, positive Anti-HBs or positive Anti-HBc). Performed locally by PCR at screening, every 12 weeks during treatment, at EOT, and Q12W for up to 6 months after the last dose of study treatment. Not required at C1D1 if performed at screening. Patients with serologic findings suggestive of HBV vaccination (antiHBs positivity as the only serologic marker) and a known history of prior HBV vaccination do not need to be tested for HBV DNA by PCR.
STUDY DRUG RANDOMIZATION					
Randomization	-	х	-	-	To be performed up to 3 business days before the first dose of study treatment on C1D1. Patients will be randomly allocated in a 1:1 ratio to receive daratumumab in combination with lenalidomide or lenalidomide alone
Study Treatment Administration	-	←X→ (thirty-six, 28-day cycles) All patients treated with daratumumab will be observed for at least 6 hours after the end of the SC injection on C1D1. If	-	-	 Daratumumab 1800 mg SC: Weekly during C1 and C2, Every 2 weeks during C3-C6, and Every 4 weeks from C7 onwards until confirmed PD, unacceptable toxicity, or until end of study treatment Refer to Section 6.2.2 related to Pre-Administration and Post-

		STUDY PHA	SES/VISI	TS ^a	
Procedure	Screening	Maintenance (Cycles 1 – 36)	ЕОТ	FOLLOW-UP (FROM THE DATE OF LAST STUDY TREATMENT UNTIL THE END OF STUDY)	Notes

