9.5.2. Clinical Laboratory Tests

9.5.2.1. Hematology, Chemistry, Pregnancy, HCV, and HBV Tests

Hematology, serum chemistry, and pregnancy tests (for women of childbearing potential) will be conducted by an on-site accredited local laboratory. The specific tests and the timing of these tests are detailed in the Time and Events Schedule – Part 1 (refer to the rows for hematology, serum chemistry, and pregnancy testing).

Note: For women of childbearing potential only: lenalidomide is a thalidomide analogue and is contraindicated for use during pregnancy. Birth defects have been observed in preclinical studies of lenalidomide similar to thalidomide in humans. Therefore, strict monitoring for pregnancy must be conducted during screening and throughout the Treatment Phase, as specified in the Time and Events Schedules. Where lenalidomide is supplied locally, patients must adhere to the local lenalidomide REMS program. Where lenalidomide is supplied centrally and no local lenalidomide REMS program exists, then patients must adhere to the lenalidomide Global Pregnancy Prevention Plan in Attachment 3. If pregnancy does occur, then study treatment should be discontinued immediately, and the patient should be referred to an obstetrician experienced in reproductive toxicity for further evaluation and counselling.

In patients with a prior history of HCV, HCV viral load will be tested in a local laboratory throughout the study as specified in the Time and Events Schedule – Part 1 rows for HCV viral load testing.

All patients will be tested for HBsAg, anti-HBs, and anti-HBc assessments performed locally prior to the first dose. For patients (in all treatment arms) with serologic evidence of prior HBV infection, HBV-DNA testing will be performed locally at screening, every 12 weeks during treatment, at EOT, and every 12 weeks for up to 6 months after last dose of study treatment. HBV-

DNA is not required at C1D1 if performed at screening. Patients with serologic findings suggestive of HBV vaccination (anti-HBs positivity as the only serologic marker) and a known history of prior HBV vaccination do not need to be tested for HBV-DNA by PCR. See Time and Events Schedule – Part 1 rows for HBV testing.

The investigator must review the laboratory results, document this review, and record any clinically relevant changes occurring during the study in the Adverse Event section of the eCRF. The laboratory reports must be filed with the source documents.

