10.2. Discontinuation of Study Treatment/Withdrawal from the Study

10.2.1. Discontinuation of Study Treatment

A patient will not be automatically withdrawn from the study if he or she must discontinue study treatment before the end of the treatment regimen; instead, the patient will enter the Follow-up Phase. The EOT Visits and Follow-up visit assessments should continue as specified in the Time and Events Schedules.

A patient's study treatment must be discontinued if the following occurs:

- The investigator believes that for safety reasons or tolerability reasons (eg, adverse event) it is in the best interest of the patient to discontinue study treatment.
- The patient becomes pregnant.
- The patient (or the patient's legally acceptable representative) withdraws consent for administration of study drug.
- The patient experiences unacceptable toxicity, including daratumumab injection-related reactions described in Section 6.2.3.
- If 3 consecutive planned doses of daratumumab are missed for reasons other than toxicity unless, upon consultation with the sponsor and the review of safety and efficacy, continuation is agreed upon.
- The patient experiences PD (please see below); loss of CR is not considered as PD.
- The patient experiences a malignancy other than multiple myeloma that cannot be treated by surgery alone (however, a patient who develops a malignancy that can be cured surgically may continue to receive the assigned study treatment and should continue to be followed for subsequent progression of multiple myeloma).

The primary reason for discontinuation of study treatment will be recorded in the eCRF.

Study treatment will continue until PD/unacceptable toxicity or until the end of study treatment, whichever occurs first. Before patients are discontinued from study treatment because of suspected PD:

- 1. The investigator (or designee) will provide documentation of PD (eg, by completing a PD form or by contacting the IWRS) as soon as possible and within 48 hours of confirmation of PD.
- 2. The sponsor's medical monitor will review the provided documentation and confirm that PD has occurred per IMWG criteria (see Section 9.3.1) and that study treatment should be discontinued.
- 3. After confirmation of PD by the sponsor, the patient will discontinue study treatment and enter the Follow-up Phase.

CONFIDENTIAL – FOIA Exemptions Apply in U.S.

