10.2.2. Withdrawal From the Study

A patient will be withdrawn from the study for any of the following reasons:

- Lost to follow-up
- Withdrawal of consent for study participation
- Death
- Sponsor terminates the study

If a patient is lost to follow-up, every reasonable effort must be made by the study-site personnel to contact the patient and determine the reason for discontinuation/withdrawal. The measures taken to follow-up must be documented.

When a patient withdraws consent before completing the study, the reason for withdrawal is to be documented in the eCRF and in the source document. Study treatment assigned to the withdrawn patient may not be assigned to another patient. Patients who withdraw will not be replaced. If a patient discontinues study treatment and withdraws from the study before the EOT Phase, EOT assessments should be obtained. If the reason for withdrawal from the study is withdrawal of consent, then no additional assessments are allowed.

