12.3. Procedures

12.3.1. All Adverse Events

All adverse events and special reporting situations, whether serious or non-serious, will be reported from the time a signed and dated ICF is obtained until 30 days (\pm 7 days) after the last dose of study treatment(s). The only exceptions are as follows (whichever occurs first):

- Patients who have withdrawn informed consent for study participation
- Patients who have received additional treatment with therapeutic intent for multiple myeloma within 30 days (\pm 7 days) after the last dose study treatment(s). For these patients, only adverse events that are considered to be possibly, probably, or definitely related to the study drug must be reported (unless the patient has been withdrawn from the study).

Serious adverse events, including those spontaneously reported to the investigator within 30 days (\pm 7 days) after the last dose of study treatment(s), must be reported using the Serious Adverse Event Form. The sponsor will evaluate any safety information that is spontaneously reported by an investigator beyond the time frame specified in the protocol.

Death and PD should not be recorded as an adverse event or serious adverse event but as the outcome of an adverse event. The event that resulted in the death should be reported as a serious adverse event.

All events that meet the definition of a serious adverse event will be reported as serious adverse events, regardless of whether they are protocol-specific assessments. Anticipated events will be recorded and reported as described in Attachment 2.

All adverse events, regardless of seriousness, severity, or presumed relationship to study treatment(s), must be recorded using medical terminology in the source document and the eCRF. Whenever possible, diagnoses should be given when signs and symptoms are due to a common etiology (eg, cough, runny nose, sneezing, sore throat, and head congestion should be reported as "upper respiratory infection"). Investigators must record in the eCRF their opinion concerning the relationship of the adverse event to study therapy. All measures required for adverse event management must be recorded in the source document and reported according to sponsor instructions.

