6.1. Adverse Events

All adverse events whether serious or non-serious, will be reported from the time a signed and dated informed consent form (ICF) is obtained until 30 days after the last dose of study treatment, until the subject withdraws consent for study participation, or until the subject starts subsequent antimyeloma therapy, whichever occurs first. Adverse Events will be recorded in standard medical terminology and graded according to the National Cancer Institute Common Terminology Criteria for Adverse Events (NCI-CTCAE), Version 5.0. The verbatim terms used in the eCRF by investigators to identify AEs will be coded using the latest Medical Dictionary for Regulatory Activities (MedDRA) coding dictionary.

Unless otherwise specified, at each level (e.g., system organ class and/or preferred term) of subject summarization in reporting the incidence of the AE, a subject is counted once if one or more events were recorded.

All summaries of AEs will be based on treatment-emergent adverse events (TEAEs). TEAEs are defined as any AE that occurs after start of the first study treatment through 30 days after the last study treatment, or the day prior to start of subsequent antimyeloma therapy, whichever is earlier; or any AE that is considered drug-related (very likely, probably, or possibly related) regardless of the start date of the event; or any AE that is present at baseline but worsens in toxicity grade during the TEAE reporting period, or after the TEAE reporting but is considered drug-related by the investigator. If the event occurs on the day of the first study treatment and either event time or time of study drug are missing, then the event will be assumed to be treatment-emergent. If the event date is recorded as partial or completely missing, then the event will be considered as treatment-emergent unless it is known to be prior to the first study treatment based on partial onset date or resolution date.

The following AE summaries will be presented by treatment group.

- An overview of TEAEs, including the number and percentage of subjects with
 - TEAEs
 - treatment-emergent SAEs
 - TEAEs related to study treatment
 - TEAEs leading to discontinuation of study treatment which includes those subjects indicated as having discontinued treatment due to an AE on the End of Treatment Disposition CRF page
 - TEAEs leading to discontinuation of any study treatment with action taken of drug withdrawn on AE CRF page

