6.3.7. Hepatitis B virus reactivation

Hepatitis B virus reactions TEAEs will be summarized by SOC and PT for all grades, Grade 3 or 4, Grade 5, and SAEs. Hepatitis B virus reactions can be identified by PT as below:

- Hepatitis viral
- Acute Hepatitis B
- Hepatitis B
- Hepatitis B reactivation
- Chronic Hepatitis B
- Hepatitis B DNA assay positive
- Hepatitis B DNA increased

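### HBV DNA testing runs about five months past the adverse-event window under conflicting recording rules, and study withdrawal after a positive HCV test is not reconciled with Protocol Section 10.2

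*Protocol*

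**What the plan says.** **HBV testing.** For patients with serologic evidence of past HBV infection, the Time and Event Schedule – Part 1 has HBV DNA tested during treatment, at EOT, and then "Q12W for up to 6 months after the last dose of study treatment". Protocol Section 9.5.2.1 gives the same follow-up timing.

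**AE recording.** Protocol Section 12.3.1 says all events, serious or not, "will be reported from the time a signed and dated ICF is obtained until 30 days" (±7) after the last dose. Later safety information is evaluated by the sponsor if an investigator reports it spontaneously. Section 9.5.1 sets the same 30-day (±7) limit. Sections 9.5 and 9.5.2.1, however, send clinically relevant changes arising during the study to the AE form. Section 12.3.2 asks for every SAE that occurs during the study.

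**SAP.** Section 6.3.7 states: "Hepatitis B virus reactions TEAEs will be summarized by SOC and PT". Section 6.1 states: "TEAEs are defined as any AE that occurs after start of the first study treatment through 30 days after the last study treatment", or to the day before subsequent antimyeloma therapy if that is earlier. A further limb admits any AE judged possibly, probably or very likely related, whatever its start date. The laboratory parameters in SAP Section 6.5 do not include HBV DNA.

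**HCV.** The schedule says patients with a history of HCV "will be withdrawn from the study if they test positive at any time during the study", and exclusion criterion 7c says the same. Protocol Section 10.2.1 says: "A patient will not be automatically withdrawn from the study if he or she must discontinue study treatment"; such a patient enters the Follow-up Phase. Section 10.2.2 opens with "A patient will be withdrawn from the study for any of the following reasons" and lists loss to follow-up, withdrawal of consent, death and termination by the sponsor. HCV is not on that list.

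**The concern.** Blood is drawn for a named adverse event of clinical interest over a period in which the protocol gives sites two different rules about recording the result. A site that works from Sections 12.3.1 and 9.5.1 stops at 30 days (±7); a site that works from Section 9.5.2.1 carries on. The HBV reactivation count then depends partly on which section each site follows. For recorded events after day 30 it also depends on the attribution given by an unblinded investigator.

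The HCV problem is of a different kind. Read literally, the schedule and criterion 7c end study participation for a randomised patient on a laboratory result that may be related to treatment. Section 10.2 keeps patients who stop treatment under observation. What is at stake is disease-progression, other-malignancy and next-line-therapy follow-up after that date. PFS is the major secondary endpoint, so follow-up that ends for this reason could be informative.

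**Working it through.** The documents state no figure to reproduce here. The check compares time windows and sets the rules side by side.

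**Inputs**
- HBV DNA monitoring after the last dose: 6 months = 6 × 30.4375 = 182.6 days (schedule; Protocol 9.5.2.1).
- AE window: 30 days, range 23 to 37 from the ±7 (Protocol 12.3.1 and 9.5.1).
- Test spacing: 12 weeks = 84 days.

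**Monitoring time outside the AE window** = 182.6 − window
- 30 days: 182.6 − 30 = 152.6 days; 152.6 / 182.6 = 84%.
- 37 days: 145.6 days; 80%.
- 23 days: 159.6 days; 87%.

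**Where the follow-up tests fall.** The protocol does not say what the 12-week interval is counted from, so three anchors were tried.
- From the last dose: days 84 and 168. Both are after day 37.
- From an EOT visit on day 30: day 30 + 84 = 114, which is after day 37. The next, day 198, is beyond 6 months.
- From the last on-treatment test, taken 0, 28, 56 or 83 days before the last dose: days 84 and 168; 56 and 140; 28 and 112; 1, 85 and 169. At least one test falls after day 37 in every case.

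The EOT test itself may be done on days 23 to 37. The time limb of the SAP definition ends at day 30 without the ±7, so a finding on days 31 to 37 can be inside the protocol window and outside that limb.

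**What happens to an HBV event arising after day 37**
1. Is it recorded? Under 12.3.1 and 9.5.1 there is no general duty. Under 9.5 and 9.5.2.1, yes if clinically relevant; under 12.3.2, yes if serious.
2. If recorded and judged at least possibly related, it is a TEAE and enters the 6.3.7 table.
3. If recorded and judged doubtful or not related, it ordinarily stays out of the table. SAP 6.5 plans no HBV DNA summary that would show it elsewhere.

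Two of the seven preferred terms in SAP 6.3.7 are HBV DNA assay findings, so the table is meant to take in assay results once they are recorded as AEs.

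**HCV.** Viral load is scheduled at C4D1, C8D1 and so on to C36D1, which is nine tests. C36D1 is day 35 × 28 + 1 = 981 of a planned 36 × 28 = 1,008 treatment days. Every scheduled test is on treatment, so a positive result arises inside the AE window. The conflict is about what follows: the schedule and criterion 7c end study participation, while 10.2.1 and 10.2.2 do not provide for that.

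**The case against.** The strongest reply is that a duty to record late HBV findings already exists. The section that schedules the tests (9.5.2.1) tells the investigator to review the results and enter relevant changes on the AE form, and 12.3.2 covers SAEs throughout the study, which includes the Follow-up Phase. A reader might otherwise infer that late reactivations are simply lost; the documents do not support that. What stands is that these sections and 12.3.1 with 9.5.1 give different end points and nothing says which governs.

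A reader might also infer that the SAP table closes at day 30. It does not: related events count whatever their start date, and Protocol Section 12.1.2 sets a low bar for a possible relationship. The gap is limited to collection and to late events judged doubtful or not related.

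On HCV, the reply is that the event is found on treatment, is reportable, and would appear in the infections table if coded to that system organ class. Persisting abnormalities and unresolved SAEs are followed after withdrawal (9.5, 12.3.2). Consent covers survival status (16.2.3), which limits the risk to OS. It is also tempting to say that the patient leaves the intent-to-treat population; that is wrong, because the full analysis set contains everyone randomised. Section 10.2.2 does not say that its list is exhaustive, and 10.2.1 only rules out automatic withdrawal. All of this stands. It leaves the loss of later PFS, other-malignancy and next-line data, and two passages that do not fit Section 10.2.

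**Conclusion.** The point holds in two limited parts.

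First, HBV DNA monitoring outlasts the AE window by about five months (about 153 of 183 days; 146 to 160 days across the ±7). In that period the recording rules conflict, and the SAP table depends on attribution in an open-label trial. This takes 6 months as 182.6 days. The finding that every post-EOT test lies beyond day 37 assumes counting from the last dose or from a day-30 EOT visit; with other anchors at least one test does.

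Second, the HCV study-withdrawal text is not reconciled with 10.2.1 and 10.2.2, and it puts later follow-up of a randomised patient at risk.

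The documents give no prevalence of past HBV or HCV infection, so the number of patients affected cannot be stated. The protocol does not explain why HBV testing extends to 6 months, and nothing here rests on a presumed reason. No effect on the primary endpoint is shown.

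**What to change.** - **Protocol 12.3.1 and 9.5.1:** state that HBV reactivation, including HBV DNA turning positive, is recorded as an AE through the last scheduled HBV DNA test. Align 9.5, 9.5.2.1 and 12.3.2 with that wording.
- **SAP 6.3.7:** count these events from first dose to that same date regardless of attribution, and show events after day 30 in a separate row.
- **HCV:** reconcile the schedule note and exclusion criterion 7c with 10.2.1 and 10.2.2. The revised text should separate the decision about study treatment, on which no view is given here, from continued collection of follow-up data.

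The cost is a short protocol clarification, a few extra AE reports and one table row. No new tests are needed, because the HBV DNA samples are already scheduled.

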treatment-emergent adverse events (TEAEs) was similar in both treatment groups (62.9% in the DRd group and 62.7% in the Rd group). Of the most frequently reported (>10%) Grade 3 or 4 adverse events, higher rates of neutropenia (DRd: 50.0%; Rd: 35.3%), lymphopenia (DRd: 15.1%; Rd: 10.7%), leukopenia (DRd: 11.0%; Rd: 4.9%), and pneumonia (DRd: 13.7%; Rd: 7.9%) were observed in the DRd group, while Grade 3 or 4 anemia occurred more frequently in the Rd group (DRd: 11.8%; Rd: 19.7%). Although Grade 4 TEAEs were reported in a higher percentage of patients in the DRd group compared with the Rd group, fewer patients in the DRd group (7.1%) discontinued study treatment due to a TEAE compared with the Rd group (15.9%); however, the percentage of patients discontinuing lenalidomide was similar in both arms.

The current study is being conducted to evaluate the MRD negativity conversion rate following the addition of daratumumab (compound number JNJ-54767414) to lenalidomide, when administered as maintenance treatment to patients with newly diagnosed multiple myeloma who have received a minimum of 4 cycles of induction therapy, have undergone HDT and ASCT within 12 months of the start of induction, are MRD positive at the time of screening, and have never been treated with an anti-CD38 antibody (ie, are anti-CD38 naïve). Further details on the overall rationale for the study, study design, assessments chosen for evaluation, and the potential risks and benefits are described in Section 3.2.

Throughout the protocol, the term "study treatment" refers to the treatments being administered for multiple myeloma and the term "sponsor" refers to the entities listed in the Contact Information page(s), which will be provided as a separate document.

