7. STUDY TREATMENT(S) COMPLIANCE

Study drug (daratumumab) will be administered by qualified staff, and the details of each administration will be recorded in the eCRF. Refer to the Commercial Prescribing Instructions for drug preparation and administration.

Patients will be provided with a diary to record intake of lenalidomide as well as pre- and postdaratumumab administration medications, if required; sites will use information to complete exposure information in the eCRF.

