14. STUDY TREATMENT INFORMATION

For the purposes of this study, study drug refers to daratumumab.

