Attachment 2: Anticipated Events

Anticipated Event

An anticipated event is an adverse event (serious or non-serious) that commonly occurs as a consequence of the underlying disease or condition under investigation (disease-related) or background regimen.

For the purposes of this study, the following events will be considered anticipated events:

- Bleeding
- Bone diseases
- Hypercalcemia
- Hyperuricemia
- Hyperviscosity syndrome
- Infection
- Renal failure or insufficiency

Reporting of Anticipated Events

All AEs will be recorded in the eCRF regardless of whether considered to be anticipated events and will be reported to the sponsor as described in Section 12.3.1, All Adverse Events. Any anticipated event that meets serious adverse event criteria will be reported to the sponsor as described in Section 12.3.2, Serious Adverse Events. Each anticipated event will be assessed by the investigator at the individual case level and if considered to be drug-related will undergo expedited reporting (if appropriate) as per applicable clinical trial legislation to Health Authorities and IRB/ECs. If an anticipated event is considered disease-related or not related to study drug the event will be exempt from expedited reporting.

To meet US regulatory clinical trial legislation, the sponsor will perform aggregate review of anticipated events as outlined below, and if determined to be drug-related will implement expedited reporting of these events to Health Authorities and IRBs/ECs. If an interim analysis of trial results leads to an unblinded, aggregate review of safety data by the study team, the sponsor may terminate the review of pre-specified anticipated events outlined above.

Safety Assessment Committee

A Safety Assessment Committee (SAC) will be established to perform reviews of pre-specified anticipated events at an aggregate level. The SAC is a safety committee within the sponsor's organization that is independent of the sponsor's study team. The SAC will meet to aid in the recommendation to the sponsor's study team as to whether there is a reasonable possibility that an anticipated event is related to the study drug based on a review of the aggregate data by arm.

Statistical Analysis

Details of statistical analysis of anticipated events, including the frequency of review and threshold to trigger an aggregate analysis of anticipated events, will be provided in a separate Anticipated Events Safety Monitoring Plan.

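### For adverse events after new myeloma therapy starts, the protocol's related-only reporting duty is tied to a term defined as daratumumab, so for non-serious events it is empty on lenalidomide alone, and the protocol and SAP give three different rules for the same days

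*Protocol*

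**What the plan says.** Protocol Section 12.3.1 requires all adverse events to be reported from consent until 30 (±7) days after the last dose of study treatment, with two exceptions. One is withdrawal of consent. The other covers "Patients who have received additional treatment with therapeutic intent for multiple myeloma within 30 days" (±7 days) of the last dose. For these patients, "only adverse events that are considered to be possibly, probably, or definitely related to the study drug must be reported".

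Section 14 states: "For the purposes of this study, study drug refers to daratumumab". Section 7 uses the term in the same way: "Study drug (daratumumab) will be administered by qualified staff". Attachment 3 switches its meaning to lenalidomide, but expressly for that attachment only. The Introduction provides a wider term, *study treatment*, for everything given for myeloma on study.

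SAP Section 6.1 says that events are reported until 30 days after the last dose, until consent is withdrawn, or "until the subject starts subsequent antimyeloma therapy, whichever occurs first". The same section counts as treatment-emergent "any AE that is considered drug-related (very likely, probably, or possibly related) regardless of the start date of the event".

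**The concern.** Within one bullet, Section 12.3.1 uses two terms. The time window runs from the last dose of *study treatment(s)*, while the relatedness filter refers to *the study drug*. If the second term has its Section 14 meaning, what must be collected after new therapy starts depends on the arm. A patient on lenalidomide alone has had no daratumumab, so no event can meet the filter. A patient on the combination can have events that do.

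The trial is open-label, and safety and tolerability form a secondary endpoint, summarised by treatment group. A collection rule that differs by arm can make the arms look different for reasons unrelated to toxicity. Lenalidomide toxicity in these days may also go unrecorded in both arms.

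**Working it through.** No arithmetic settles this; it is a comparison of texts.

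**Step 1. What must be reported for an event after new therapy starts, within 30 (±7) days of the last dose, if *study drug* means daratumumab (Section 14)?**

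| Event | Daratumumab + lenalidomide | Lenalidomide alone |
|---|---|---|
| Non-serious, related to daratumumab | Required | Cannot arise |
| Non-serious, related to lenalidomide only | Not required | Not required |
| Non-serious, related to neither | Not required | Not required |
| Serious | Required | Required |

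The last row rests on two texts: the paragraph of 12.3.1 that sends serious events in this window to the Serious Adverse Event Form, and Section 12.3.2, which requires every serious event during the study with no relatedness filter.

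The difference between arms lies in the first row. An event judged possibly related to both drugs is required on the combination. The same clinical event on lenalidomide alone, judged possibly related to lenalidomide, is not.

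**Step 2. Is the Section 14 meaning applied throughout?** No. Section 6.3 asks that toxicity be attributed to a specific study drug and then discusses dose adjustment for lenalidomide only. Section 6.3.3, on lenalidomide, speaks of study drug-related toxicity. If the term covers both drugs, lenalidomide-related events are required in both arms and the asymmetry disappears. Sites could follow either reading.

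**Step 3. Which rule governs these days?**

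| Source | Non-serious events after new therapy starts |
|---|---|
| Protocol 12.3.1, exception | Only those related to the study drug |
| Protocol 9.5.1 | All, to 30 (±7) days after the last dose of any component; no new-therapy exception |
| SAP 6.1, first sentence | None; reporting has stopped |

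Section 12.3.1 also has a general sentence that all events are to be recorded whatever their relationship to study treatment. Read as overriding, it would leave the exception with nothing to do, so it does not resolve the matter.

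**Step 4. Can the difference reach the tables?** Yes, if such events are collected. The SAP's treatment-emergent definition admits drug-related events regardless of start date. A daratumumab-related event collected under 12.3.1 after new therapy would therefore enter the treatment-emergent and treatment-related summaries. A comparable lenalidomide-related event might never have been collected. This also conflicts with the first sentence of SAP 6.1, which ends reporting at that point.

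**Step 5. Causality grades.** Section 12.1.2 has five grades: not related, doubtful, possible, probable and very likely. The filter in 12.3.1 names *definitely*, which is not one of them, and omits *very likely*. SAP 6.1 uses *very likely*.

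**Step 6. Length of the window.** It opens when new therapy starts, after the last dose, and closes 30 (±7) days after that dose. It is thus at most 30 + 7 = 37 days per patient.

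**The case against.** The strongest defence is that this is loose wording with little practical effect, and much of that stands.

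- The clause sets a minimum and forbids nothing. Sites may report more.
- Section 12.1.1.4 defines association by study treatment(s), and 12.3.1 asks investigators for the relationship to study therapy. A site could well apply the clause to lenalidomide. The amendment history shows that the Section 14 sentence replaced supply wording to meet Canadian drug provision requirements, which suggests that it was never aimed at safety reporting. Its words nevertheless cover the whole study, and it is the only express definition outside Attachment 3.
- An end-of-treatment visit is due as soon as possible before next-line therapy, so earlier events should be captured in both arms.
- If the first sentence of SAP 6.1 governs, collection stops in both arms and no asymmetry reaches the tables.

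Three stronger readings are tempting, and the documents do not support them. A reader might infer that the lenalidomide-alone arm can report nothing; the serious-event rules and the minimum nature of the clause rule that out. A reader might try to size the imbalance from the progression-free survival assumptions. Those events include deaths, and the plan gives neither the share of patients starting new therapy in the window nor any event rate within it. A reader might also extend the point to Attachment 2, where "If an anticipated event is considered disease-related or not related to study drug the event will be exempt from expedited reporting". That governs expedited regulatory reporting, not collection: all events are still recorded, and a safety committee reviews anticipated events in aggregate by arm.

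**Conclusion.** The point holds in a limited form. As defined in the protocol, the related-only duty is empty for non-serious events on lenalidomide alone and live for daratumumab-related events on the combination. Non-serious events related only to lenalidomide fall outside it in both arms. Separately, and whichever meaning of *study drug* is taken, three incompatible rules cover the same days.

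An effect on the safety tables is possible, not certain. It requires that 12.3.1 rather than SAP 6.1 drives collection, that sites read *study drug* as Section 14 defines it, and that lenalidomide-related events are in fact left out. It concerns non-serious events only, in patients who start new myeloma therapy within 30 (±7) days of the last dose. Its size cannot be derived from the documents. The case for changing the text is that the rule should not depend on arm and that the correction is cheap.

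**What to change.** 1. In Section 12.3.1, replace *study drug* in the exception with *any component of study treatment (daratumumab or lenalidomide)*, and use the Section 12.1.2 grades: possible, probable or very likely.
2. Limit the definition in Section 14 to that section.
3. Align Section 9.5.1 and the first sentence of SAP 6.1 with the amended 12.3.1, so that related events after new therapy are collected and counted in the same way in both arms.

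The cost is protocol and SAP wording, plus a few more related events recorded in the lenalidomide arm. Dosing and patient management are untouched.
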